We will utilize published models for predicting mortality in patients with AAH to stratify patients

based on severity. Although previous studies of treatment for severe AAH utilized 30-day mortality as an endpoint, 6-month mortality is a more relevant outcome, in part because most transplantation programs require 6 months of abstinence before active listing. Furthermore, the number of deaths between 6 and 12 months in abstinent patients is low compared to the number in the first 6 months. Patients will be stratified into those with Model of End-stage Liver Disease (MELD) score ≤ 20 and MELD ≥ 20 . Those stratified into the moderate group are described in a separate application. The primary difference between the Maddrey discriminant function (DF) and the MELD is that the latter includes creatinine. We propose to use the MELD score to stratify for severity but require that patients in the severe group also have a DF > 32 , to avoid including patients with chronic kidney disease, not hepatorenal syndrome.

Specific Aim 1 = Randomized controlled trial for severe acute alcoholic hepatitis: MELD ≥ 20

: Patients with severe AAH will be randomized equally into two arms. Patients with MELD 20-25, patients with MELD 26-31, and patients with MELD \geq 32 will be randomized separately into two equal arms to ensure comparable severity in the three groups. The trial will also be double-blinded by re-packaging all oral medications into capsules to ensure that each group receives an equal number of capsules each day for the entire duration of the study.

Patients will be treated with pentoxifylline 400 mg three times daily for 28 days PLUS zinc supplements for a total of 6 months (Group A) or methylprednisolone 32 mg daily for 28 days PLUS placebo capsules daily for the remaining 5 months (Group B). An injection of either anakinra (100 mg), Group A or a placebo (Group B) will be given subcutaneously each day for 14 days. Patients, investigators and physicians involved in the care of the patients will be blinded as to the treatment.

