The primary outcome will be 6-month mortality. Secondary outcomes will include 30 and 90 day mortality; changes in MELD score at 30, 90 and 180 days and changes in gut mucosal permeability measured by serum tests. Serum endotoxin levels and serum cytokine profiles (IL-1, TNF1, etc.) will also be measured in both groups at baseline, 2, 7, 30, 90 and 180 days. The attached table indicates the timing of samples performed both for research purposes and for insuring standard of care for the subjects.

Specific Aim 2 = Natural history of severe acute alcoholic hepatitis: MELD ≥ 20 :

Patients with severe AAH who decline to be randomized but consent to prospective data collection and minimal risk non-invasive studies (blood drawing and urine collection). We will also look to enroll subjects with alcoholic hepatitis/alcoholic liver disease who are not eligible for the Drug Trial but who are willing to provide specimens and data, valuable information regarding the natural history of alcoholic hepatitis and the aims noted above. Specimens including blood, urine, stool, and liver tissue if a liver biopsy is done as part of subject's standard treatment, will be collected from subjects participating in this sub study. This will be a one-time collection of specimens to follow the procedure of the Study Day 0 for all enrolling participants.

Specific Aim 3 = Subjects will be asked for a DNA blood draw during the first day of the study.

All human subjects will be patients with a clinical presentation consistent with acute alcoholic hepatitis (AAH). The trial is designed to test the hypothesis that AAH results from inflammation triggered by gut derived endotoxins and other bacterial products as a consequence of increased permeability of the gut mucosa. Patients with AAH will be stratified by disease severity as determined by the Model for End-Stage Liver Disease (MELD) score and enrolled in one of two randomized controlled trials.

Subject population: The total subject population will be 260 patients with alcoholic hepatitis, 130 in each disease severity group (moderate disease is defined as MELD ≤ 20 and severe disease as MELD 20-25, MELD 26-31, and MELD > 32). The age range will be 21 – 70 years old. The health status of the population will be that of a group with significant acute clinical presentation from alcoholic liver disease.

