Statistical analysis plan: Our primary analysis of change in MELD score from baseline to 30 days will be an unadjusted comparison of change (Day 30 – Baseline) using a standard two- group t-test at a two-sided alpha level of 0.05 with appropriate adjustment for unequal variances. We will also conduct secondary analyses to further investigate factors that influence the change as well as adjust for any imbalances in patient characteristics and covariates between treatment groups. Our initial model will be an Analysis of Covariance (ANCOVA) model with change in MELD score as the outcome and with treatment group (0=control, 1=probiotic) and baseline MELD score as predictors. Additional models will include patient characteristics such as age, gender, time since diagnosis as well as other covariates such as ALT, AST, and other laboratory measures at baseline. Finally, as it is likely that MELD score can be calculated throughout the duration of the study, we will use mixed models to analyze the longitudinal MELD score data. Mixed (random effects) models are used to adjust for the inherent correlation among the laboratory (and, thus, MELD score) measures on the same patient. We will consider treatment as a fixed effect, but most other factors as random effects. The model will also include a time metric, so that, rather than the change from baseline, we can use the coefficients of the times as estimates of the change from baseline (time=0), adjusted for the other factors in the model. So, for example, if MELD score is calculated at Days 0, 7, 14, 21, and 30, the model might look like: $MELDt = \beta_0 + \beta_1*tx + \beta_2*gender + \beta_3*age + \beta_4*Day7 + \beta_5*Day14 + \beta_6*Day21 + \beta_7*Day30$ where $MELDt$ = MELD score at time t ($t=0, 7, 14, 21, 30$), $\beta_0 \dots \beta_7$ = regression coefficients, tx = treatment (0=control, 1=probiotic), $gender$ = patient's gender (0=female, 1=male), age =patient's age at last birthday, $Day7$ = MELD score at Day 7 (0=No, 1=Yes), ..., $Day30$ = MELD score at Day 30 (0=No, 1=Yes). This implies that the baseline MELD score is represented by $Day7=Day14=Day21=Day30=0$. Interpreting this model, which makes maximum use of all available MELD scores, the coefficient β_4 is the estimate of the change in MELD score from baseline to Day 7, β_5 is the estimate of the change in MELD score from baseline to Day 14, etc. By combining all of the information into a single model, we can adjust the MELD score changes for other factors as well as test for a difference in the slopes of the changes between the two treatment groups. The model can, of course, be extended beyond 30 days if measures are available. The fit of the model will be assessed primarily through the likelihood ratio test of the fitted model to the intercept only model. All coefficients will be tested for significance at a critical level of $p=0.05$.

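### The example MELD mixed model in the moderate-trial plan has no treatment-by-day terms, so it cannot test the between-arm slope difference that the plan assigns to it

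*Combined protocol and SAP*

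**What the plan says.** Section 13 contains a statistical analysis plan for the moderate (probiotic) trial. The primary analysis is a two-group t-test of the change in MELD from baseline to day 30. An ANCOVA of the same change follows, and last comes a mixed model for all available MELD scores. The plan explains that, with time in the model, "we can use the coefficients of the times as estimates of the change from baseline".

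The example equation assumes MELD at days 0, 7, 14, 21 and 30. It has eight coefficients: intercept, treatment (0 control, 1 probiotic), gender, age, and indicators for days 7, 14, 21 and 30, with baseline as the reference. It has no product of treatment and day.

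The plan says that the Day 7 coefficient "is the estimate of the change in MELD score from baseline to Day 7", and reads the later days the same way, without mention of arm. It then says that combining the information in a single model allows the changes to be adjusted for other factors "as well as test for a difference in the slopes of the changes between the two treatment groups". Fit is to be judged mainly by the "likelihood ratio test of the fitted model to the intercept only model". It adds: "All coefficients will be tested for significance at a critical level of" 0.05.

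On scope, section 3 (Concise Summary of the Project) states: "Those stratified into the moderate group are described in a separate application". For the severe trial, section 3 lists "changes in MELD score at 30, 90 and 180 days" among the secondary outcomes. The severe-trial analysis plan in section 13 gives no longitudinal method for them.

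**The concern.** A difference in slopes between arms is a treatment-by-time interaction. The plan attributes a test of it to a model with main effects only. If the example were fitted as printed, the longitudinal MELD analysis could not answer the question set for it. Every coefficient is to be tested, and treatment is the only coefficient that involves arm, so it could be taken for the effect on change, which it does not estimate.

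**Working it through.** **Inputs.** From section 13, moderate-trial sample size: mean changes 5.0 (control) and 8.0 (probiotic), so a difference of 3.0; SD 5.559; 54 per arm; two-sided alpha 0.05; power 80%. From the example: days 0, 7, 14, 21 and 30. The documents give no within-patient correlation and no shape of effect over time. Those below are assumptions, as are complete data and equal correlation between visits.

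**1. The plan's own figure.** 3.0 / (5.559 × √(2/54)) = 2.80, which gives power 0.801 by the normal approximation (0.794 with the t distribution). The plan's 108 patients are reproduced when 5.559 is read as the SD of the change.

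**2. The contrast the plan wants.** Difference in change at day d = [(probiotic, day d) − (probiotic, day 0)] − [(control, day d) − (control, day 0)]. In the printed equation each bracket reduces to the same day coefficient, so the contrast is 0 at days 7, 14, 21 and 30, whatever the data. With four treatment-by-day products added (12 coefficients), the contrast at each day equals that day's product coefficient.

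**3. What the printed coefficients estimate.** With balanced complete data, the treatment coefficient has expectation equal to the mean of the five visit differences:

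- linear divergence: (0 + 0.7 + 1.4 + 2.1 + 3.0)/5 = 1.44, or 0.48 of 3.0
- immediate constant effect: (0 + 3 + 3 + 3 + 3)/5 = 2.40, or 0.80 of 3.0
- waning, mild: (0 + 4.0 + 4.0 + 3.5 + 3.0)/5 = 2.90, below 3.0
- waning, steep: (0 + 6.0 + 6.0 + 4.5 + 3.0)/5 = 3.90, above 3.0

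With 0 at baseline and 3.0 at day 30, the mean exceeds 3.0 only if the differences at days 7, 14 and 21 sum to more than 5 × 3.0 − 3.0 = 12, that is, average more than 4.0. In every case the Day 30 coefficient is (5.0 + 8.0)/2 = 6.5, one value for both arms.

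**4. Power, for orientation only.** Take 5.559 as the SD of change, so residual variance v = 5.559²/2 = 15.45 and variance per visit is v/(1 − ρ). The standard error of the treatment coefficient is √((2/54) × [v/(1 − ρ)] × (1 + 4ρ)/5).

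| | ρ = 0.3 | ρ = 0.5 | ρ = 0.7 |
|---|---|---|---|
| SE of treatment coefficient | 0.600 | 0.829 | 1.204 |
| Its power, linear divergence | 0.67 | 0.41 | 0.22 |
| Its power, immediate effect | 0.98 | 0.83 | 0.51 |
| Treatment-by-Day30 contrast | 0.80 | 0.80 | 0.80 |

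The joint 4-df treatment-by-visit test has noncentrality (54/2) × Σ(d − mean d)²/v, where d is the visit difference. This is 9.60 (linear) or 12.58 (immediate), for power of 0.70 or 0.82.

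The constant 0.80 follows from reading 5.559 as the SD of change. If it is instead the SD of MELD at one visit, the SD of change is 5.559 × √(2(1 − ρ)), and the Day30 contrast has power 0.66, 0.80 and 0.95 at the three correlations. The other figures would move too, except at ρ = 0.5, where the two readings coincide.

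**5. The fit check.** The likelihood ratio compares the fitted model with an intercept-only model. The interaction is absent from both, so the statistic cannot show that it is missing.

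**6. Is the term supplied elsewhere?** No treatment-by-time term appears anywhere in section 13. The fold-change plan also names only treatment and time as predictors. Random effects do not supply it: they have mean zero, and treatment is declared fixed.

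**The case against.** The strongest reply is that the equation is a sketch. It is offered as an example, it leaves out the random effects and error term that the surrounding text calls for, and the aim is stated in words. An analyst who follows that aim would add the interaction. This limits the consequence but does not remove the mismatch, because the slope test is attributed to this single model and no other specification is given.

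The reply on scope also stands. The analysis is the last-listed secondary one, for a group assigned to a separate application, and the t-test and ANCOVA already compare day-30 change between arms.

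Three stronger readings are tempting, and the documents do not support them:

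- A reader might infer that the plan presents the treatment coefficient as the day-30 effect. It interprets only the day coefficients, so the figures in step 3 show the cost of a possible misreading, not of a stated one.
- A reader might infer a fixed direction of error, for instance that the coefficient is always too large when an effect wanes. Step 3 shows both directions.
- A reader might infer that the severe trial's MELD analysis has the same defect. The model is the only longitudinal MELD method given and is said to be extendable beyond 30 days, but nothing commits the severe trial to it.

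**Conclusion.** The point holds as an internal contradiction: the example model cannot perform the test that the same paragraph claims for it. This rests on algebra alone and needs no assumption about correlation, effect shape or SD.

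The expectations of 1.44 and 2.40 against 3.0 rest on complete balanced data and the stated shapes. The power figures rest further on assumed correlations and on the reading of 5.559, so they are illustrative.

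The scope is minor. It would be wrong to conclude that the moderate trial lacks a valid test of MELD change, or that the severe trial's mortality comparison is affected: the day-30 t-test, the ANCOVA and the log-rank test do not depend on this equation.

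**What to change.** Add treatment-by-visit terms to the MELD mixed model and name the contrast to be tested: either treatment-by-Day30 or the joint treatment-by-visit test. If the model is reused for the severe trial's MELD change at 30, 90 and 180 days, include the same terms there. They would not by themselves deal with MELD values missing because of death, which matter when planned 6-month control survival is 0.64.

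The cost is one or two sentences of plan wording, with no extra data or patients. The example gains four parameters. There is also a loss of power against a main-effect term if the effect is immediate and within-patient correlation is low: 0.80 to 0.82 against 0.98 at a correlation of 0.3, with 5.559 read as the SD of change. That main-effect test, however, addresses an average offset and not the difference in change.

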The proposed study represents the culmination of a planning process involving the members of the proposed Executive Committee and other co-investigators. The criteria for selecting the proposed treatments included current FDA approval for other indications and a known safety profile in other disease states so that a beneficial treatment(s) could be brought forward for a phase III clinical trial and/or transform treatment for AAH, a condition for which the current treatment paradigm is unsatisfactory. **The selection of the medications was based on the hypothesis that the syndrome of AAH results from inflammation and release of IL-1, TNF 1, and other pro-inflammatory cytokines, triggered by gut derived endotoxins and other bacterial products as a consequence of increased permeability of the gut mucosa.**

[figure not shown]
The standard of care (corticosteroids) is recommended by both the American Association for the Study of Liver Diseases and the American College of Gastroenterology in published practice guidelines^(5, 16). A second agent, pentoxifylline, provides protection from development of acute kidney injury⁽¹⁷⁾. Both agents improve short-term survival (28 day) but 6 month mortality remains high, 30% – 50%⁽¹⁸⁾. In this clinical trial, corticosteroids (methylprednisolone 32 mg/d for 28 days) will be compared with a drug regimen designed to decrease inflammation (interleukin-1 receptor antagonist for 28 days) and improve gut permeability (oral zinc for 6 months). In addition the study drug regimen will include pentoxifylline to protect against acute kidney injury (AKI, hepatorenal syndrome).

3. Concise Summary of the Project:

Our study will test the hypothesis that the syndrome of acute alcoholic hepatitis (AAH) results from severe inflammation and dysregulated cytokines, providing the “second hit” that causes an acute deterioration. We further hypothesize that gut derived endotoxins and other bacterial products trigger inflammation and are a consequence of increased permeability with altered gut barrier function. Steroid monotherapy is not effective in all patients with AAH. Consequently, our studies will utilize compounds that have the potential to improve gut barrier function (both in moderate and severe disease) AND to reduce the associated inflammation (severe disease) AND to prevent the development of hepatorenal syndrome and other organ failure (severe disease).

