
Sample size for study of patients with severe acute alcoholic hepatitis

Using the Lakatos approach(19) to estimating the sample size for a log-rank test, we find that a two-sided logrank test with an overall sample size of 130 patients (65 patients each of the control and treatment groups) achieves 80.0% power at a 0.05 significance level to detect a hazard ratio of 0.4447 when the proportion surviving at 6 months in the control group is 0.64 and 0.82 in the treatment group. The total study duration is 2.5 years of which subject accrual (entry) occurs in the first 2 years. We assume that the accrual pattern is uniform throughout the accrual period and that the proportion drop-out in each group is 0.10 during the 6 months with no treatment cross-overs. As a sensitivity analysis of these estimates, we used the Lachin- Foulkes approach⁽²⁰⁾, a slightly less flexible approach and, with the same assumptions as above, we estimate 53 patients in each group, reasonably close to the Lakatos estimates. Thus, to be conservative in our estimates, we will set our

sample size as 130 patients total or 65 patients in each treatment group. PASS II (NCSS, Kaysville, Utah) was used for all sample size calculations⁽²¹⁾.

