Statistical analysis plan: Our primary analysis of this outcome will be the unadjusted log-rank test of the Kaplan-Meier survival estimates for the two treatment groups at a two-sided alpha level of 0.05 with survival censored at 6 months. Secondary analysis will use a Cox proportional hazards regression model (with survival censored at 6 months) to adjust the treatment difference in survival for patient characteristics (e.g., age, gender, time since diagnosis) and other covariates (e.g., ALT, AST, other lab measures). Predictors will be added to the model using reference cell coding, as with the mixed models above. The Cox model generates estimates of the hazard ratio for each factor compared to the reference level; e.g., for male patients vs. female patients, assuming gender = 1 for male and 0 for females, a hazard ratio of 1.25 indicates that males have a 25% higher probability of death overall by 6 months compared to females. We can also add time-dependent covariates to the model, such as ALT levels at 2 and 4 months, to estimate their predictive value for mortality. To assess the fit of the model, we will use Nagelkerke's R² constructed from the ratio of the likelihoods for the fitted model to the intercept only model. As further secondary analysis, we can eliminate the survival censoring

at 6 months and test the overall survival throughout the duration of follow-up.

General analysis plan for experiments with fold change as the outcome: Initial analyses will be descriptive in nature, allowing for investigation of appropriate normalization approaches. Initial comparative analyses of fold-change between treatment groups (or between other groups of interest) will be through a standard two-group t-test at the p=0.05 level with appropriate adjustment for unequal variances. If the fold change data are longitudinal in nature, we will use mixed (random effects) models to estimate the change in fold-change over time. In these models, fold-change at each time point will be the outcome with treatment (or other group indicator) and time as predictors. Additional patient characteristics can be added to the model to create adjusted estimates of treatment (or other group) differences. Mixed models can adjust for the correlation due to measures within patients and due to repeated microarrays at each time point.

References

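### The stated 80.0% power with 130 patients does not hold for the primary log-rank test censored at 6 months; power is about 62–63%

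*Combined protocol and SAP*

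**What the plan says.** Section 13, in the sample-size paragraph for severe disease, uses the Lakatos method. It states that a "two-sided logrank test with an overall sample size of 130 patients" (65 per arm) "achieves 80.0% power at a 0.05 significance level to detect a hazard ratio of 0.4447 when the proportion surviving at 6 months" is 0.64 on control and 0.82 on treatment. On timing it says: "The total study duration is 2.5 years of which subject accrual (entry) occurs in the first 2 years". Accrual is uniform, drop-out is 10% per arm over the 6 months, and there is no cross-over.

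A Lachin-Foulkes calculation follows as a sensitivity check: "with the same assumptions as above, we estimate 53 patients in each group, reasonably close to the Lakatos estimates". The larger figure is then adopted with the words "Thus, to be conservative in our estimates".

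The analysis plan for the severe trial, in the same section, makes the primary analysis an unadjusted log-rank test "at a two-sided alpha level of 0.05 with survival censored at 6 months". Removing that censoring is offered only as a further secondary analysis.

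**The concern.** The sample-size paragraph describes a study that runs for 2.5 years. The primary test uses at most 6 months of each patient's time. Log-rank power depends on the number of deaths that enter the test, and the plan's own survival proportions fix that number closely: at most 65 × (0.36 + 0.18) = 35.1 expected deaths, before any drop-out. That looked too few for 80% power at a hazard ratio of 0.4447.

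If so, the trial has a much larger chance than stated of missing a halving of mortality. Section 12 says a negative outcome would spare others a treatment without added benefit. A null result from an underpowered test cannot carry that reading. Calling 130 conservative adds to the false assurance.

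**Working it through.** **Inputs** (Section 13, severe trial): two-sided α = 0.05; 65 per arm; 6-month survival 0.64 and 0.82; drop-out 10% in 6 months; accrual 2 years, total 2.5 years; primary test censored at 6 months. Constant hazards are my assumption, because the plan gives no hazard shape.

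**Hazard ratio.** ln(0.82)/ln(0.64) = 0.4447. The plan's figure reproduces.

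**Hazards per year.** Control −ln(0.64)/0.5 = 0.893; treatment −ln(0.82)/0.5 = 0.397; drop-out −ln(0.90)/0.5 = 0.211.

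**The plan's sample sizes, with follow-up to 2.5 years.**
- Lachin-Foulkes: N = 104.4, or 52.2 per arm, which rounds up to the printed 53.
- Lakatos: N = 98.5, and power at 130 is 89.6%. The printed 130 at 80.0% does not reproduce.

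**Deaths needed at 80% power (Schoenfeld).** 4(1.96 + 0.8416)²/(ln 0.4447)² = 4 × 7.849/0.6568 = 47.8.

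**Deaths expected by 6 months.** With λ the death hazard and δ the drop-out hazard, the probability of an observed death is [λ/(λ+δ)] × [1 − exp(−(λ+δ) × 0.5)]. This gives 0.343 on control and 0.171 on treatment, so 65 × (0.343 + 0.171) = 33.4.

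**Schoenfeld power.** Φ(√33.4/2 × 0.8104 − 1.96) = Φ(0.382) = 64.9%.

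**Lachin-Foulkes at 6 months.** N = [1.96√(4λ̄²/Ē) + 0.8416√(2λ₁²/E₁ + 2λ₂²/E₂)]²/(λ₁ − λ₂)², where E is the death probability above and λ̄ = 0.645, Ē = 0.262. The two terms are 4.935 and 2.143, so N = 7.078²/0.4957² ≈ 204, or 102 per arm.

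**Results for the planned test at 130 patients:**

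| Method | Power, 10% drop-out | Power, no drop-out | N for 80% power (10% drop-out) |
|---|---|---|---|
| Lakatos | 62.1% | 64.2% | 198.5 |
| Lachin-Foulkes | 61.1% | 63.2% | 203.9 |
| Schoenfeld | 64.9% | 67.0% | – |
| Freedman | 60.3% | – | – |
| Log-rank simulation, 20,000 trials | 63.2% | 65.0% | – |
| Log-rank simulation, 40,000 trials | 62.6% | 64.7% | – |

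Simulating 99 per arm gives 80.8%, which confirms the size of about 198. A one-sided 0.05 test would reach only 73.3% (Lakatos).

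**Effect detectable at 130 patients.** With control survival 0.64 and 10% drop-out, 80% power is reached at treatment survival 0.857 by Lakatos (hazard ratio 0.345) and 0.861 by Lachin-Foulkes. Simulation gives 80.7% at 0.855.

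**Do the two printed sizes share inputs?** Of the settings tried, Lakatos matched 130 only with a total time of 2 years (N = 130.6; 79.8% power), which contradicts the printed 2.5 years and also counts deaths after 6 months. Lachin-Foulkes at 2 years gives 137.3, not 106. On common inputs Lachin-Foulkes was slightly the larger each time (104.4 against 98.5; 137.3 against 130.6; 203.9 against 198.5). The plan prints the reverse order, 106 against 130.

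**The case against.** **The source of 130 is not known.** The 2-year match is an inference. Section 3 (Sampling plan) says the size allowed for drop-out, non-evaluable results and possible non-representativeness of the source database. The moderate trial is inflated by dividing by 0.80, and 104/0.80 = 130. This stands as a rival explanation of where 130 came from. Only the 53 per group is shown to rest on deaths after 6 months. Neither explanation restores power, because the 62–63% is computed from 130 enrolled patients and the stated survival.

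**The sample-size paragraph alone is not optimistic.** On its printed 2.5 years, power at 130 is about 90%. That is true, and it locates the fault: the shortfall comes from combining that paragraph with a primary test that discards follow-up after 6 months.

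**The hazard need not be constant.** A strongly front-loaded hazard (Weibull shape 0.5, same 6-month survival) gives 63.3%, so this does not matter.

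**Control mortality may exceed 36%.** Section 2 quotes 30% to 50% at 6 months. Holding the hazard ratio at 0.4447, Lakatos power with 10% drop-out runs from about 54% to 78%. At the 50% end with no drop-out it is 79.7% (Schoenfeld 81.5%). So at the very top of the range power comes close to 80%, but the plan specifies 36%.

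**Nothing in the test changes.** The error neither biases the estimate nor raises the type I error. That is correct; what is wrong is the claim about what the trial can detect.

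**Conclusion.** The concern holds. For the primary test as written, 130 patients give about 33 deaths and about 62–63% power (60–65% across methods), against the stated 80.0%. The type II error is about 37–38%, not 20%. Even with no drop-out, power is only 63–67%. About 198 patients (Lakatos) to 204 (Lachin-Foulkes) would be needed for 80% power at 0.64 versus 0.82.

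This rests on the plan's control survival of 0.64 and on proportional hazards; the shape of the hazard has little effect. The Lachin-Foulkes check does not support the size, since it reproduces on a 2.5-year horizon and gives about 102 per group at 6 months. The two printed sizes do not appear to share one set of assumptions. How the Lakatos 130 arose cannot be settled from the documents, and the conclusion does not depend on it.

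**What to change.** Rewrite the severe-trial sample-size paragraph for the log-rank test censored at 6 months:

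- State that with survival 0.64 versus 0.82 and 10% drop-out, 130 patients give about 33 deaths and about 62–63% power. Equivalently, power is about 80% for 0.64 versus about 0.855–0.86 (hazard ratio about 0.34–0.35).
- State for information that 80% power for 0.64 versus 0.82 would need about 198 patients by Lakatos.
- Correct the Lachin-Foulkes check to about 102 per group.
- Document the Lakatos inputs and reconcile them with the printed 2.5 years. Drop the claim of identical assumptions unless both methods are rerun on the same inputs.
- Keep the word conservative only in the sense of the larger of two estimates, not as a description of 130 for the 6-month test.

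The cost is one rewritten paragraph and a less favourable power statement. The endpoint, test, α and enrolment can stay as they are.
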